## 6 Baseline Characteristics

Baseline characteristics will be summarized using descriptive statistics for continuous variables or frequency counts and percentages for categorical variables. Two-sided 95% confidence intervals will also be presented.

A summary table will be reported with key baseline characteristics, including subject demographics, admission functional assessments, and lesion evaluation results.

## 7 Subject Disposition

The number of subjects in the following categories will be recorded:

- Enrolled subjects
- Completed and discontinued subjects
- ITT population
- PP population

Frequency counts and percentages will also be tabulated on the reasons for registry discontinuation: adverse events, death, exclusion for medical reasons, exclusion from registry by investigator, LTFU, withdrawal of consent, or other causes.

## 8 Effectiveness Analysis

### 8.1 Primary Effectiveness Analysis

The primary efficacy outcome is the rate of retreatment through one-year follow-up. Frequency counts and percentages will be reported for the subjects who required retreatment. A two-sided 95% binomial proportion confidence interval will be developed for the retreatment rate using a normal approximation to the binomial. All primary and secondary efficacy endpoint analyses will be run on both the intent-to-treat (ITT) population and the per-protocol (PP) population.

### 8.2 Secondary Effectiveness Analysis

Frequency counts and percentages will be reported for the two secondary efficacy outcomes:

- **Ability to achieve adequate occlusion at immediate post-procedure:** Defined as the proportion of subjects achieving adequate occlusion based on the investigator's assessment given anatomical and other considerations at immediate post-procedure.

This endpoint applies to the investigator's Yes/No assessment on whether adequate occlusion was achieved and not the Raymond-Roy Occlusion Scale. Frequency counts and percentages will be reported for this proportion. Two-sided 95% binomial proportion confidence intervals will be developed, using a normal approximation to the binomial.

- **Re-access with guidewire due to catheter kickout:** This endpoint applies to catheter kickout while using SMART/PC 400/POD coils and not other adjunctive coils. Frequency counts and percentages will be reported for the proportion of subjects experiencing 0, 1, 2, and  $\geq 3$  kickout events. Two-sided 95% binomial confidence intervals with a normal approximation to the binomial will be presented for each frequency count.

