##### **3.2.1 The Endpoints are:**

- Retreatment through follow-up
- Procedural device-related serious adverse events at immediate post-procedure
- Ability to achieve adequate occlusion - based on investigator's adjudication of adequate occlusion given anatomical and other considerations immediate post-procedure
- Number of times re-access with guidewire was required due to catheter kickout

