## 9 Subgroup Analysis

The following subgroup analyses will be performed for the primary and secondary effectiveness and safety endpoints:

- Actual adjunctive treatment used: Balloon, Stent, Other, None
- Age: < 65,  $\geq 65$
- Aneurysm location: Extradural ICA, ICA, ACA, MCA, Posterior Circulation, Venous Circulation, Other
- Aneurysm size: Small (Up to 10 mm in the largest diameter), Large (> 10 mm to 25 mm in the largest diameter), Giant (> 25 mm in the largest diameter)
- Aneurysm status: Ruptured, Unruptured
- Lesion nature: Aneurysm, Arteriovenous malformation, Fistula, Other
- Lesion treatment technique: Constructive, Deconstructive
- Neck width: Small neck (< 4 mm neck width), Wide neck ( $\geq 4$  mm Neck Width or Dome-to-Neck ratio (defined as Dome Width / Neck Width)  $< 2$ )
- Vessel treatment at admission: Initial treatment, Retreatment

For re-access with guidewire due to catheter kickout, which is analyzed based on 0, 1, 2, and  $\geq 3$  kickout events, subgroup analyses will be performed using the Wilcoxon rank-sum test for subgroup variables with two levels and the Kruskal-Wallis test for subgroup variables with more than two levels. For the other three categorical endpoints, subgroup analysis will be performed using Fisher's Exact test.

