## Secondary Effectiveness Analysis

| Secondary Effectiveness Analysis   |  |                             |               |
|--|--|-----------------------------|---------------|
| Secondary Endpoints   |  | All Subjects (N = N) | 95% CI |
| Adequate Occlusion at Immediate Post-Procedure                                     |  | X.X% (n/N)                  | (X.X%, X.X%)  |
| Raymond Scale Class I  |  | X.X% (n/N)                  | (X.X%, X.X%)  |
| Raymond Scale Class II   |  | X.X% (n/N)                  | (X.X%, X.X%)  |
| Raymond Scale Class III  |  | X.X% (n/N)                  | (X.X%, X.X%)  |
| Re-Access Attempts with Guidewire due to Catheter Kickout (Smart/PC 400/POD)       |  |                             |               |
| 0  |  | X.X% (n/N)                  | (X.X%, X.X%)  |
| 1  |  | X.X% (n/N)                  | (X.X%, X.X%)  |
| 2  |  | X.X% (n/N)                  | (X.X%, X.X%)  |
| ≥ 3  |  | X.X% (n/N)                  | (X.X%, X.X%)  |
| Additional Analyses   |  |                             |               |
| Re-Access Attempts with Guidewire due to Catheter Kickout (Other Adjunctive Coils) |  |                             |               |
| 0  |  | X.X% (n/N)                  | (X.X%, X.X%)  |
| 1  |  | X.X% (n/N)                  | (X.X%, X.X%)  |
| 2  |  | X.X% (n/N)                  | (X.X%, X.X%)  |
| ≥ 3  |  | X.X% (n/N)                  | (X.X%, X.X%)  |
| First Framing Coil Conformed to Lesion Morphology                                  |  |                             |               |
| Completely Conformed   |  | X.X% (n/N)                  | (X.X%, X.X%)  |
| Partially Conformed  |  | X.X% (n/N)                  | (X.X%, X.X%)  |
| Compartmentalized  |  | X.X% (n/N)                  | (X.X%, X.X%)  |
| N/A  |  | X.X% (n/N)                  | (X.X%, X.X%)  |
| Packing Density  |  | X.X% (n/N)                  | (X.X%, X.X%)  |
| Occlusion at One Year (Aneurysms)  |  |                             |               |
| Class I  |  | X.X% (n/N)                  | (X.X%, X.X%)  |
| Class II   |  | X.X% (n/N)                  | (X.X%, X.X%)  |
| Class III  |  | X.X% (n/N)                  | (X.X%, X.X%)  |
| Occlusion of Lesion at One Year (Non-Aneurysms)                                    |  |                             |               |
| Better (Progressive Occlusion)   |  | X.X% (n/N)                  | (X.X%, X.X%)  |
| Stable   |  | X.X% (n/N)                  | (X.X%, X.X%)  |

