### Subgroup Analysis: Actual Adjunctive Treatment Used

| Subgroup Analysis   | Balloon    | 95% CI       | Stent      | 95% CI       | Other      | 95% CI       | None       | 95% CI       | P-Value |
|---|------------|--------------|------------|--------------|------------|--------------|------------|--------------|---------|
| Retreatment through Follow-Up                             | X.X% (n/N) | (X.X%, X.X%) | X.XXX   |
| Adequate Occlusion at Immediate Post-Procedure            | X.X% (n/N) | (X.X%, X.X%) | X.XXX   |
| Re-Access Attempts with Guidewire due to Catheter Kickout |            |              |            |              |            |              |            |              |         |
| 0   | X.X% (n/N) | (X.X%, X.X%) | X.XXX   |
| 1   | X.X% (n/N) | (X.X%, X.X%) | X.XXX   |
| 2   | X.X% (n/N) | (X.X%, X.X%) | X.XXX   |
| ≥ 3   | X.X% (n/N) | (X.X%, X.X%) | X.XXX   |

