## Secondary Effectiveness Analysis

| Subject   | Was Adequate Occlusion Achieved? | Occlusion of the Aneurysm  | Re-Access with Guidewire due to Catheter Kickout while Using SMART/PC 400/POD | Re-Access with Guidewire due to Catheter Kickout while Using Other Adjunctive Coils | First Framing Coil Conformed to Lesion Morphology                       | Packing Density | Occlusion of the Aneurysm at One Year  | Occlusion Grading of Lesion at One Year (Non-Aneurysm)  |
|-----------|----------------------------------|--|---|---|---|-----------------|--|---|
| 99999-999 | Yes
No                        | Not Applicable (no aneurysm treated)
Class I
Class II
Class III
Not done, explain: | Yes
No   | Yes
No
N/A  | Completely Conformed
Partially Conformed
Compartmentalized
N/A | X%              | Not Applicable (no aneurysm treated)
Class I
Class II
Class III
Not done, explain: | Better (Progressive Occlusion)
Stable
Worse (Recanalization)
Not Applicable (aneurysm treated)
Not done, explain: |

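### The kickout subgroup tests compare per-subject counts without regard to the number of coils used, and two appendix shells do not match the endpoint or its planned test

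*SAP*

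**What the plan says.** Protocol 3.2.1 defines the endpoint as a count: "Number of times re-access with guidewire was required due to catheter kickout". It names no denominator. SAP 8.2 limits it to the sponsor's coils ("This endpoint applies to catheter kickout while using SMART/PC 400/POD coils and not other adjunctive coils") and summarises it by subject: "Frequency counts and percentages will be reported for the proportion of subjects experiencing 0, 1, 2, and" three or more events.

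For subgroups, SAP 9 states that "subgroup analyses will be performed using the Wilcoxon rank-sum test for subgroup variables with two levels and the Kruskal-Wallis test" is used for variables with more than two levels. That is one test per subgroup variable, with no offset, stratification or other allowance for coil number. Aneurysm size has three levels (small, large, giant), so its planned test is Kruskal-Wallis.

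Four places in the SAP appendix carry the item:

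- The Secondary Effectiveness and Sensitivity Analysis table shells use rows 0, 1, 2 and ≥3. The first also has a block for other adjunctive coils under additional analyses.
- The subgroup shell has the same four rows under "Re-Access Attempts with Guidewire due to Catheter Kickout" and, as extracted, a p-value on each.
- The subject listing has a column "Re-Access with Guidewire due to Catheter Kickout while Using SMART/PC 400/POD" whose only values are Yes and No.

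SAP 14 tells programmers to repeat the subgroup table in the format of the mock shell. No SAP table or listing shows a number of coils.

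**The concern.** Protocol Section 2 presents kick-back as something that happens at the end of delivering a coil, and credits the coil's progressive softness with reducing it. On that account each coil delivered is a new opportunity for the event. If one subgroup receives more coils per subject, it will tend to show more kickouts even when every coil behaves identically. A small p-value for aneurysm size could then be read as a finding about the device when it reflects exposure. A real per-coil difference could equally be hidden by an opposite difference in coil number.

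The two shell points are separate and do not cause the exposure problem. A Yes/No value cannot produce the rows 1, 2 and ≥3. Four p-values per subgroup variable are not what SAP 9 specifies.

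**Working it through.** The documents give no kickout rate, coil number or size mix, so there is no figure of the plan's to reproduce. All inputs below are assumptions, varied over a range.

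**1. Why exposure matters.** With risk q per coil and c coils, the chance of at least one kickout is 1 − (1 − q)^c. At q = 2%:

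- 4 coils: 1 − 0.98^4 = 7.8%
- 8 coils: 1 − 0.98^8 = 14.9%
- 12 coils: 1 − 0.98^12 = 21.5%

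The per-coil risk is the same in all three.

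**2. The planned test on aneurysm size.** Assumed: 800 small, 150 large and 20 giant; identical q in all groups; counts capped at ≥3; Kruskal-Wallis, two-sided 5%. Share of simulated registries with p < 0.05:

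| Coils (small/large/giant) | q = 1% | q = 2% | q = 3% |
|---|---|---|---|
| Equal | about 5% | about 5% | about 5% |
| 5 / 7 / 9 | 24% | 36% | 44% |
| 4 / 8 / 12 | 63% | 84% | 95% |

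Repeat runs, with coil numbers either fixed or varying between subjects, stayed within about four percentage points of these figures.

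**3. Two-group check against a per-coil test.** Assumed: 800 versus 200 subjects, coil numbers varying around the stated means, the same q in both groups, 1,000 runs.

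| Mean coils | Wilcoxon, q = 1% / 2% / 5% | Events per coil, all q |
|---|---|---|
| 5 vs 5 | about 5% throughout | 4–5% |
| 5 vs 7 | 23% / 32% / 61% | about 4% |
| 5 vs 10 | 67% / 89% / about 100% | 4–6% |

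**4. Does the rank test still see coil behaviour?** Yes. With a mean of 5 coils in both groups and per-coil rates of 2% versus 4%, it rejects in 90% of runs (2% versus 3%: 43%). It can also miss a real difference: 4% × 5 coils and 2% × 10 coils both give 0.20 expected events per subject, and the test rejects in only 5%.

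**5. The other-coil block.** At least 75% of implanted coils must be Smart, PC 400 or POD, so other coils number at most 25/75 = one third of the Smart family in any subject. Without a denominator, the two blocks are on different exposures.

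**6. Shells against text.**

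- Listing: Yes/No. Tables: 0, 1, 2, ≥3. The first cannot yield the second.
- Subgroup shell: four p-values. SAP 9: one test. If the four were independent, the chance of at least one p < 0.05 under no difference would be 1 − 0.95^4 = 18.5%. The levels are dependent, so this is only indicative.

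**The case against.** The per-subject count is the protocol endpoint, and the SAP implements it faithfully. How often a patient's procedure needed re-access is a legitimate description, the registry is single-arm and mainly descriptive, and nothing says the subgroup results will be read per coil. This stands, and it is the reason to keep the count table and the rank test.

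The sizes rest wholly on assumed inputs. The documents do not show that coil number differs by aneurysm size, still less by age or rupture status. Protocol Section 2 says PC 400 has up to four times the volume per unit length of most other coils and presents it for larger aneurysms, which could narrow any difference. This also stands, so the simulated figures are conditional.

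An offset model has its own assumption: risk proportional to coil number. The protocol links kick-back with dense packing, so later coils may carry a different risk. The model therefore belongs beside the rank test, not in its place.

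The subgroup shell was read from a PDF, and its rows have fewer cells than its header. A single p-value cell spanning four rows may have been split in extraction. That point should be checked against the source file.

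A reader might infer three stronger things that the documents do not support:

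- *The subgroup tests measure coil number instead of coil behaviour.* They measure a mixture, and step 4 shows that they respond to behaviour when coil numbers are equal.
- *The endpoint cannot be computed.* Only the listing is Yes/No. The table shells use counts, the protocol's procedural data include access attempts at the target location, and the case report form is not available to settle it.
- *The plan makes an unfair comparison of Smart-family with other coils.* SAP 8.2 excludes other coils from the endpoint, and the appendix shows them as an additional display without a test.

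**Conclusion.** The point holds as a limit on what the kickout subgroup results can support. The analysis of the protocol endpoint is not itself in error. If coil number rises with aneurysm size and per-coil risk is 1% to 3% in every group, the planned test would reject in about 24% to 44% of registries under a modest gradient and in about 63% to 95% under a steep one, against a nominal 5%. Where coil numbers are equal, there is no inflation. The direction follows from the missing denominator; the size depends on coil numbers and a kickout rate that the documents do not give.

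The listing mismatch needs no assumption: Yes/No does not carry the information that the tables require. The four p-values conflict with SAP 9 if the shell reads as extracted. This is a secondary endpoint in a descriptive registry, so the changes are worthwhile and cheap rather than critical.

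**What to change.** 1. Keep the 0, 1, 2, ≥3 table and the rank tests as the analysis of the protocol endpoint.
2. Add re-accesses per coil, separately for the Smart family and for other coils.
3. Add a supportive Poisson or negative binomial model for each subgroup variable, with log(number of Smart-family coils) as offset. State that coils implanted stand in for coils attempted, and that the model takes risk as proportional to coil number.
4. Change the listing field to an integer count, and confirm that the case report form records one.
5. Show one p-value per subgroup variable for this endpoint in the subgroup shell.

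The cost is SAP and shell wording plus one supportive model with its proportionality assumption. Implanted coil numbers should already be to hand, because SAP Section 1 defines the 75% rule by number of coils and the protocol's schedule of assessments collects the proportion of SMART coils. SAP Section 1 places sign-off before database lock, so the change can be made before then.

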## 9 Subgroup Analysis

The following subgroup analyses will be performed for the primary and secondary effectiveness and safety endpoints:

- Actual adjunctive treatment used: Balloon, Stent, Other, None
- Age: < 65,  $\geq 65$
- Aneurysm location: Extradural ICA, ICA, ACA, MCA, Posterior Circulation, Venous Circulation, Other
- Aneurysm size: Small (Up to 10 mm in the largest diameter), Large (> 10 mm to 25 mm in the largest diameter), Giant (> 25 mm in the largest diameter)
- Aneurysm status: Ruptured, Unruptured
- Lesion nature: Aneurysm, Arteriovenous malformation, Fistula, Other
- Lesion treatment technique: Constructive, Deconstructive
- Neck width: Small neck (< 4 mm neck width), Wide neck ( $\geq 4$  mm Neck Width or Dome-to-Neck ratio (defined as Dome Width / Neck Width)  $< 2$ )
- Vessel treatment at admission: Initial treatment, Retreatment

For re-access with guidewire due to catheter kickout, which is analyzed based on 0, 1, 2, and  $\geq 3$  kickout events, subgroup analyses will be performed using the Wilcoxon rank-sum test for subgroup variables with two levels and the Kruskal-Wallis test for subgroup variables with more than two levels. For the other three categorical endpoints, subgroup analysis will be performed using Fisher's Exact test.

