### Adjunctive Treatment

| Adjunctive Treatment              | All Subjects (N = N) | 95% CI       |
|-----------------------------------|----------------------|--------------|
| Adjunctive Technology Pre-Planned | X.X% (n/N)           | (X.X%, X.X%) |
| Stent-Assisted Coiling            | X.X% (n/N)           | (X.X%, X.X%) |
| Balloon-Assisted Coiling          | X.X% (n/N)           | (X.X%, X.X%) |
| Other                             | X.X% (n/N)           | (X.X%, X.X%) |
| Adjunctive Technology Used        | X.X% (n/N)           | (X.X%, X.X%) |
| Stent-Assisted Coiling            | X.X% (n/N)           | (X.X%, X.X%) |
| Balloon-Assisted Coiling          | X.X% (n/N)           | (X.X%, X.X%) |
| Other                             | X.X% (n/N)           | (X.X%, X.X%) |

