### Adjunctive Treatment

| Subject   | Adjunctive Technology Pre-Planned | Planned Adjunctive Treatment                                | Adjunctive Technology Used | Actual Adjunctive Treatment                                 |
|-----------|-----------------------------------|---|----------------------------|---|
| 99999-999 | Yes
No                         | Stent-Assisted Coiling
Balloon-Assisted Coiling
Other | Yes
No                  | Stent-Assisted Coiling
Balloon-Assisted Coiling
Other |

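### The adjunct subgroup is formed only by what was actually used, which can be a response to procedural events; the pre-planned adjunct is recorded but enters no subgroup

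*SAP*

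**What the plan says.** SAP section 9 opens with "The following subgroup analyses will be performed for the primary and secondary effectiveness and safety endpoints" and lists the adjunct grouping as "Actual adjunctive treatment used: Balloon, Stent, Other, None". Kickout re-access is compared across these four levels by "the Kruskal-Wallis test for subgroup variables with more than two levels". The rest are covered by "For the other three categorical endpoints, subgroup analysis will be performed using Fisher's Exact test"; by elimination these are retreatment, adequate occlusion and procedural device-related SAEs. No covariate adjustment is stated. The appendix shell, "Subgroup Analysis: Actual Adjunctive Treatment Used", uses the same four columns and one p-value column. It has no SAE row, although the section 9 text includes safety.

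The registry holds both versions of the variable. The Adjunctive Treatment mock table summarises "Adjunctive Technology Pre-Planned" and "Adjunctive Technology Used" separately, each by type. The matching mock listing has a per-subject column "Planned Adjunctive Treatment" beside the actual treatment. No subgroup uses the planned field, and no table crosses plan with use.

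**The concern.** Most section 9 groupings, such as age, lesion size or rupture status, are fixed before the first coil is placed. Actual adjunct use is not. If an adjunct is added because of an intraprocedural event or the difficulty behind it, the subject's group depends on the outcome being compared. The Balloon or Stent column gains an event and the None column loses one, even if adjuncts have no effect.

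Two places in the protocol make this plausible without showing that it happens. The SAE definition counts an event as serious if it led to an intervention to stop permanent impairment, so one unplanned device could both help qualify the event and change the group. The introduction says that catheter kick-back can prevent complete embolization, which ties catheter events to procedural outcome.

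At stake is the reading of one subgroup table with p-values that may be published. A reader could take None as the performance of the coils alone, when complications that led to an adjunct have left that column.

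**Working it through.** The plan gives no figure for planned, actual or unplanned adjunct use, so there is no stated result to reproduce. The check has three steps.

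**Step 1: can the endpoint precede the grouping?**

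| Endpoint | Timing in the SAP | Can it prompt index adjunct use? |
|---|---|---|
| Device-related SAE (10.1) | Within 24 hours of arterial puncture | Yes, if it occurs during the procedure; no, if later in the window |
| Kickout re-access (8.2) | While registry coils are in use | Yes |
| Adequate occlusion (8.2) | Judged immediately post-procedure | No; the adjunct comes first and may raise the rate, or mark a difficult case |
| Retreatment (8.1) | Through one-year follow-up | No; only shared causes can link them |

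**Step 2: expected rates for the SAE endpoint.** From SAP section 2: N = 1,000 and p = 1.7%. Assumed, not in the documents:
- q, the share with a planned adjunct: 30% or 50%
- b, the share of subjects without a planned adjunct who have an SAE and receive an adjunct: 0% to 50%
- c, the same share among those without an SAE: 0% or 5%

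Every planned adjunct is taken as used, and planned use has no true association with SAEs.

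- Used: events = Npq + Np(1−q)b; subjects = Nq + Np(1−q)b + N(1−p)(1−q)c
- None: events = Np(1−q)(1−b); subjects = N minus the Used subjects

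Worked case, q = 30%, b = 10%, c = 0:
- Planned: 300 × 0.017 = 5.1 SAEs. Not planned: 700 × 0.017 = 11.9 SAEs, of which 1.19 move.
- Used: (5.1 + 1.19)/(300 + 1.19) = 6.29/301.19 = 2.09%
- None: (11.9 − 1.19)/(700 − 1.19) = 10.71/698.81 = 1.53%
- Ratio 1.36

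| b (with SAE) | c (no SAE) | Used v None, q = 30% | Ratio | Used v None, q = 50% | Ratio |
|---|---|---|---|---|---|
| 0% | 5% | 1.53% v 1.79% | 0.85 | 1.62% v 1.79% | 0.91 |
| 10% | 0% | 2.09% v 1.53% | 1.36 | 1.87% v 1.53% | 1.22 |
| 10% | 5% | 1.87% v 1.61% | 1.16 | 1.78% v 1.61% | 1.10 |
| 25% | 0% | 2.67% v 1.28% | 2.08 | 2.12% v 1.28% | 1.65 |
| 25% | 5% | 2.39% v 1.35% | 1.78 | 2.02% v 1.35% | 1.50 |
| 50% | 0% | 3.61% v 0.86% | 4.21 | 2.53% v 0.86% | 2.95 |
| 50% | 5% | 3.25% v 0.90% | 3.60 | 2.41% v 0.90% | 2.67 |

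If b = c, both rates stay at 1.70% and the ratio is 1. The distortion comes from the difference between b and c, not from unplanned use as such.

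**Step 3: effect on the test.** In 2,000 simulated data sets per setting, balloon, stent and other were pooled into one used-versus-None Fisher test, a simplification of the planned four-level test. The proportions with p < 0.05 under no true association were:

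| b | c | q = 30% | q = 50% |
|---|---|---|---|
| 0% | 0% | 3.6% | 3.9% |
| 25% | 0% | 31% | 14% |
| 25% | 5% | 20% | 10% |

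Grouping by plan returns 1.70% v 1.70%, a ratio of 1.00 and the first row of this table, because no subject changes group after the event.

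**The case against.** The strongest case is that the SAP's choice is open and legitimate. It says actual use, and describing outcomes by the treatment delivered is normal in a post-market registry. SAP section 5 calls the results primarily descriptive. The test is one comparison across four levels, with no named contrast against None and no decision tied to it. The primary and secondary analyses run on the whole ITT and PP populations, so no headline result changes. The mock listing already shows plan and use side by side for each subject. Planned use is not randomised either. All of this stands. It limits the point but does not remove it: the p-value is still printed, and readers of a summary table do not work through a listing of 1,000 subjects.

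A reader might also infer something stronger: that devices placed to rescue a coil problem define the Balloon and Stent groups, and that every comparison is driven by its own endpoint. The documents do not support this. Those groups hold all actual use, planned use included. Nothing states why an unplanned adjunct is used or how often. Retreatment comes after the index procedure and cannot cause adjunct use in it. For occlusion, an adjunct that works could push the rate up, so the sign is not fixed.

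**Conclusion.** The point holds in limited form. Followed exactly, SAP section 9 can give a p-value for 24-hour device-related SAEs or kickout re-access that partly reflects adjuncts used in response to events. For the other two endpoints, only confounding of uncertain direction (occlusion) or confounding by difficulty or indication (retreatment) can be claimed.

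The size is unknown. The range of about 0.85 to 4.2 for the SAE ratio shows how sensitive the comparison is to facts the plan does not tabulate; it does not estimate the bias. Only the 1.7% rate and the 1,000 subjects come from the documents. This is an inexpensive improvement to a secondary table, not a flaw in the primary analyses.

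**What to change.** In SAP section 9 and the subgroup shell:

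1. Add the same subgroup analysis by pre-planned adjunct (Balloon, Stent, Other, None), using the field already in the Adjunctive Treatment table and listing.
2. Add one planned-by-actual cross-tabulation, with the four endpoints shown for subjects with unplanned use. Include the SAE endpoint, which the present shell lacks. State how a subject with both a balloon and a stent is classified, since the SAP does not.
3. Keep the actual-use table, labelled descriptive and not causal.

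The cost is SAP wording and one or two tables, with no new data. The planned grouping describes strategy rather than the device in place. It removes reclassification by the event but not confounding by indication, such as lesion size, neck width or rupture status, so the added table needs that caveat too.
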